1.0 PROTOCOL SYNOPSIS

Title	An Open-Label Clinical Study to Assess the Performance of the Dialyzer with Endexo™ in End-Stage Renal Disease Subjects
Protocol Number	Endexo-001
Study Type	Open-label single-arm clinical trial
Investigational Products	
Dialyzer with Endexo™ ("F5"), Fresenius Medical Care North AmericaOptiflux® dialyzer (F160NR), Fresenius Medical Care North America (cleared under 510(k) number K152367)
Proposed Indication	The dialyzers with Endexo are a series of single-use, high-flux dialyzers intended for treatment of patients with acute or chronic renal failure when conservative therapy is judged to be inadequate. The dialyzers with Endexo must be used in conjunction with dialysis machines equipped with ultrafiltration control and are to be used only as directed by a physician.
Study Objectives	
The primary objective of the study is to collect data on the performance of the dialyzer with Endexo when used to perform hemodialysis (HD) in End-Stage Renal Disease (ESRD) subjects.
 
The secondary objective is to collect and summarize adverse events with the dialyzer with Endexo when used to perform HD in ESRD subjects.

Study Design	This is a prospective, sequential, multi-center, open-label study with subjects on thrice-weekly (in-center) HD. After a Screening Period, there will be 12 HD treatments on the Optiflux dialyzer (Optiflux Period), followed by 38 HD treatments on the dialyzer with Endexo (Endexo Period), and then a Follow-up Visit.

Study Population	The study population will consist of ESRD subjects who are a minimum of 22 years of age, have been prescribed in-center thrice weekly HD continuously for at least 180 days prior to the date of signed informed consent, and have been prescribed the Optiflux F160NR dialyzer continuously for at least 30 days prior to the date of signed informed consent.
Total Number of Subjects	15-24 enrolled subjects, to achieve at least 12 subjects with a minimum of 36 HD treatments per subject on the dialyzer with Endexo
Total Number of Sites	3-4 (United States)
Estimated Duration of Study	
Each subject will participate in the study for a maximum of 22 weeks.
 
The Screening Period is up to 4 weeks.
 
The Optiflux Period is 12 HD treatments on the Optiflux dialyzer (4 weeks in duration). The Endexo Period is 38 HD treatments on the dialyzer with Endexo (approximately 13 weeks in duration).
 
There will be an in-center Follow-up Visit within 1 week of the subject's last HD treatment in the study.
 
After the subject's last HD treatment in the study, the subject will resume HD with his/her physician-prescribed dialyzer.

Inclusion Criteria	
A subject who signed the ICF must meet all the following inclusion criteria in order to be eligible for enrollment in the study:
 
 1. Must be an adult, defined as having had a 22nd birthday on or before the date of signed informed consent 2. Has been prescribed in-center thrice-weekly HD continuously for at least 180 days prior to the date of signed informed consent 3. Has been prescribed the Optiflux F160NR dialyzer continuously for at least 30 days prior to the date of signed informed consent 4. Has a prescribed HD treatment time \geq180 minutes (3 hours)

	
and ≤270 minutes (4.5 hours) at the time of signed informed consent
 
 5. Has been on heparin anticoagulation for dialysis and has had no change in heparin prescription within 14 days prior to the date of signed informed consent 6. Has a most recent single pool Kt/V (spKt/V) ≥ 1.2 within 45 days prior to the date of a signed informed consent 7. Has a most recent hemoglobin ≥ 9 g/dL within 45 days prior to the date of a signed informed consent 8. Has a most recent platelet count $\geq 100,000/\text{mm}^3$ within 45 days prior to the date of a signed informed consent 9. A female of childbearing potential must have a negative serum pregnancy test at the time of screening and agree to use an acceptable method of contraception during the study
Exclusion Criteria	
A subject who signed the ICF is excluded from the study if any of the following criteria are met:
 
 1. Use of citric acid concentrate (such as Citrasate[®]) at the time of signed informed consent 2. Known allergic reactions to Endexo 3. Hospitalization within 30 days prior to the date of signed informed consent 4. Presence of active malignancy, congestive heart failure New York Heart Association (NYHA) Class III or IV, or liver cirrhosis 5. Are receiving or have received chemotherapy / radiation therapy / plasmapheresis therapy within 90 days prior to the date of signed informed consent 6. Are receiving antibiotics or have used antibiotics within 14 days prior to the date of signed informed consent 7. Are currently enrolled in or have completed any other investigational product study within 30 days prior to the date of signed informed consent

	8. Has a life expectancy of less than 1 year
Study Endpoints	
The primary endpoint is to collect data on the in vivo ultrafiltration coefficient (K_{uf}) of the dialyzer with Endexo during the first study use at 15 minutes (± 5 minutes) after the recorded start of HD.
 
The secondary endpoints include collecting the following data on the dialyzer with Endexo and the Optiflux dialyzer:
 
 • The number of any adverse events and device-related adverse events • Urea Reduction Ratio (URR) and $spKt/V$ (calculated from pre- and post-HD BUN) for the first study use of the dialyzers • Pre- and post-HD albumin and beta-2-microglobulin for the first study use of the dialyzers
Additional Assessments	
The following data will be collected on the dialyzer with Endexo and the Optiflux dialyzer:
 
 • Complement activation (C3a, C5a, SC5b-9) during the first study use of the dialyzer, collected pre-HD and at 30 minutes (± 10 minutes) after the recorded start of HD • Thrombus scoring, performed at the end of dialyzer use for every dialyzer used in the study. 
The graded scoring method has been adopted from:
 
Dorsch et al. A multi-center, prospective, open-label, 8-week study of certoparin for anticoagulation during maintenance hemodialysis--the membrane study BMC Nephrology 2012 Jun 28;13:50. doi: 10.1186/1471-2369-13-50.
 
Laville et al. Results of the HepZero study comparing heparin-grafted membrane and standard care show that heparin-grafted dialyzer is safe and easy to use for heparin-free dialysis. Kidney Int. 2014 Dec ;86(6):1260-7. doi: 10.1038/ki.2014.225. Epub 2014 Jul 9.
 
 • URR and $spKt/V$ (calculated from pre- and post-HD BUN), every 3-4 weeks • Saline flushes and saline infusions during Optiflux and Endexo Periods 
 ○ Total volume (mL) per treatment, time of

	
administration and the reason
 
The following data will be collected on the dialyzer with Endexo only:
 
• Collect data on TMP and UFR for calculating the in vivo ultrafiltration coefficient (K_{uf}) of the dialyzer with Endexo at 15 minutes (± 5 minutes) after the recorded start of HD during Visits 24, 27 and 30
Data Collection	
The data listed below will be collected in the study.
 
• Demographics• Medical History (and Historical Laboratory Values)• Concomitant Medications• Physical Exam, Vital Signs, Body Measurements (height, weight)• Adverse Events and Serious Adverse Events• Device Deficiencies• Laboratory Assessments• HD Prescription, HD Treatment Data, and HD Treatment-related Medications• Machine Readings of Ultrafiltration Rate and Transmembrane Pressure for K_{uf} estimation• Thrombus Scoring• Collection of time of administration and volume (mL) per saline flush and saline infusion during each study visit under Optiflux and Endexo periods
Sample Size Determination	
The sample size of 15-24 subjects is based on FDA's Guidance for Industry and CDRH Reviewers: Guidance for the Content of Premarket Notifications for Conventional and High Permeability Hemodialyzers (August 7, 1998), which recommends that data be collected for a minimum of 12 subjects receiving 36 treatments each.

Statistical Methods	
Descriptive statistics (n, mean, standard deviation, median, minimum and maximum) will be presented for continuous endpoints. Frequency and percent will be presented for categorical endpoints. Any missing values of an endpoint will be treated as completely missing at random and will not be imputed.
 
Study analysis populations:
 
• Safety population (spop): Subjects who sign the ICF, are eligible, are enrolled in the study, and have at least one HD treatment with the dialyzer with Endexo.• Analysis population (apop): Subjects who are in the spop, and have a minimum of 36 HD treatments with the dialyzer with Endexo. 
Analysis for primary endpoint:
 
- For the K_{uf} for the dialyzer with Endexo, descriptive statistics will be presented. A 95% confidence interval will be calculated if appropriate. 
Analysis for secondary endpoints:
 
- For URR and spKt/V for the first study use of both dialyzers, descriptive statistics will be presented, and a 95% confidence interval will be calculated if appropriate.- For albumin and beta-2-microglobulin, the relative percent change $\{((\text{pre-HD} - \text{post-HD})/\text{pre-HD}) \times 100\}$ will be calculated. Descriptive statistics will be presented for the pre-HD and post-HD laboratory values and the relative percent change. The 95% confidence intervals will be calculated if appropriate.- Adverse events and device-related events per treatment will be calculated. The 95% confidence intervals will be derived if appropriate. 
Analysis for additional assessments:
 
- For the measurements of complement activation, the relative percent change $\{((30 \text{ minutes after the recorded start of HD} - \text{pre-HD})/\text{pre-HD}) \times 100\}$ will be calculated. Descriptive statistics will be presented for the "pre-HD" and "30 minutes after the recorded start of HD" laboratory values and the relative percent change. The 95% confidence intervals will be calculated if appropriate.- For thrombus formation:
• the number of subjects and percentages, and the number of HD treatments in each period for each grade category will be presented, and,
----------------------------	--

	
the proportion of treatments with full dialyzer clotting will be calculated for each subject in each period. Descriptive statistics of the proportions will be presented. A 95% confidence interval of the proportions will be calculated if appropriate.- As done for the analysis of the secondary endpoints, descriptive statistics will be presented for URR and spKt/V, and a 95% confidence interval will be calculated if appropriate.
Safety Monitoring	
All adverse events and serious adverse events will be captured from the time the subject signs the ICF until the subject completes or withdraws from the study.
 
The site investigator must inform the Sponsor of every SAE, within 24 hours of becoming aware of the occurrence.
 
The study medical monitor will evaluate and monitor safety of the subjects during the course of the study.
 
If the Sponsor determines that an unanticipated adverse event or serious adverse event presents an unreasonable risk to the subjects, the Sponsor will terminate the study as soon as possible.

## 1. STUDY OBJECTIVES

### 1.1. Primary Objective

The primary objective of the study is to collect data on the performance of the dialyzer with Endexo when used to perform hemodialysis (HD) in end stage renal disease (ESRD) subjects.

### 1.2. Secondary Objective

The secondary objective is to collect and summarize adverse events with the dialyzer with Endexo when used to perform HD in ESRD subjects.

## 2. STUDY DESIGN

### 2.1. General Description

This is a prospective, sequential, multi-center, open-label study with subjects on thrice-weekly (in-center) hemodialysis treatment.

Each subject will participate in a screening period, Optiflux period, Endexo period, and a follow-up visit.

- Screening Period

Screening, which will be up to 4 weeks in duration, begins with signing of the informed consent form (ICF). After the Screening Period is completed (with eligibility verified), the subject is enrolled and can proceed to the Optiflux Period.

- Optiflux period

The Optiflux Period is 12 HD treatments (visits 1 to 12) on the Optiflux dialyzer (4 weeks in duration). A maximum of two missed treatments are permitted within visits 2 to 11. The visit 12 cannot be missed during the Optiflux period.

- Endexo period

The Endexo period is 38 HD treatments on the dialyzer with Endexo (approximately 13 weeks in duration). The visit 13 cannot be missed. A maximum of four missed treatments are permitted within Visits 14-50.

- Follow-up visit

An in-center Follow-up visit is to be conducted within 1 week of the last scheduled study HD treatment.

### 2.2. Discussion of Study Design, Including the Choice of Control Groups

The design is based on FDA's Guidance for Industry and CDRH Reviewers: *Guidance for the Content of Premarket Notifications for Conventional and High Permeability Hemodialyzer* (August 7, 1998). A period of 4 weeks using Optiflux, which was prescribed currently, are added in prior to the use of the test product. The measurements in Optiflux period for each subject can serve as the control for comparisons as needed.

### **2.3. Method of Assigning Subjects to Treatment Groups**

N/A

### **2.4. Blinding**

N/A

### **2.5. Determination of Sample Size**

The sample size of 15-24 subjects is based on FDA's Guidance for Industry and CDRH Reviewers: *Guidance for the Content of Premarket Notifications for Conventional and High Permeability Hemodialyzer* (August 7, 1998), which recommends that data be collected for a minimum of 12 subjects receiving 36 treatments each.

## **3. CHANGES IN THE CONDUCT OF THE STUDY OR PLANNED ANALYSES**

### **3.1. Changes in the Conduct of the Study**

Protocol amendment 2:

- Added in the time of administration and reason for saline flush, and
- Collected TMP and UFR at 15 minutes ( $\pm 5$  minutes) after the recorded start of HD during visits 24, 27 and 30.

### **3.2. Changes in the Planned Analyses**

- Additional listing for reasons of saline flush. The percent of using saline to treat clotting or clotting related will be calculated if applicable.
- Additional  $K_{uf}$  will be calculated and summarized for visits 24, 27 and 30.

## **4. EFFICACY AND SAFETY ENDPOINTS**

### **4.1. Primary Endpoint(s)**

The primary endpoint is to collect data on the *in vivo*  $K_{uf}$  of the dialyzer with Endexo during the first use at 15 minutes ( $\pm 5$  minutes) after the recorded start of HD.  $K_{uf}$  can be derived from the Ultrafiltration Rate and the Transmembrane Pressure (TMP) as follows:

$$K_{uf} (\text{mL/hr/mmHg}) = \text{UF Rate} (\text{mL/hr}) / \text{TMP} (\text{mmHg})$$

#### **4.2. Secondary Endpoint(s)**

The secondary endpoints include collecting the following data on the dialyzer with Endexo and the Optiflux dialyzer:

- The number of any adverse events and device-related adverse events.
- Urea Reduction Ratio (URR) and spKt/V (calculated from pre- and post-dialysis BUN) for the first study use of the dialyzers
- Pre- and post-HD serum albumin and  $\beta_2$ -microglobulin for the first use of dialyzers, visit 1 for Optiflux and visit 13 for dialyzer with Endexo.

#### **4.3. Additional Assessments**

The following data will be collected on the dialyzer with Endexo and the Optiflux dialyzer.

- Complement activation (C3a, C5a, SC5b-9) during the first study use of the dialyzer, collected pre-HD and at 30 minutes ( $\pm 10$  minutes) after the recorded start of HD,
- Thrombus scoring, performed at the end of dialyzer use for every dialyzer used in the study,
- Urea Reduction Ratio (URR) and spKt/V every 3-4 weeks,
- Total volume (mL) of saline flush for each treatment, frequency and rate per HD treatment when using to treat clotting during HD.

### **5. STATISTICAL METHODS**

#### **5.1. General Methodology**

There are multiple observations of one measurement for each subject in each period. All analyses will be performed at the subject level i.e., take average of multiple observations first of the measurement for each subject then analyze/summarize on subject averages.

Descriptive statistics (n, mean, standard deviation, median, minimum, and maximum) will be presented for continuous endpoints. Frequency and percent will be presented for categorical endpoints. Any missing values of an endpoint will not be imputed. All data entered collected will be listed.

#### **5.2. Analysis Methods for Endpoints**

If adequate, 95% confidence interval will be calculated for each period (Optiflux or Endexo). For comparisons, if adequate, paired-t tests may be performed between periods (Optiflux vs. Endexo) for continuous endpoints, McNemar's tests may be employed for categorical endpoints.

For  $\beta_2$ -microglobulin, the laboratory results for post dialysis will be corrected for ultrafiltration using the formula in Bergström and Wehle (1987).

$$\text{Corrected value} = \frac{\text{Uncorrected value}}{1 + \Delta W/(0.2PW)},$$

where  $\Delta W$  = pre-dialysis weight – post dialysis weight, PW is the post dialysis weight.

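### SAP 5.2 permits McNemar's test between periods of 12 and 38 treatments without defining the yes/no; if that is 'any event in the period', unequal exposure alone can make Endexo look worse

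*SAP*

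**What the plan says.** SAP 5.2 makes between-period testing optional. It states "For comparisons, if adequate, paired-t tests may be performed between periods (Optiflux vs. Endexo) for continuous endpoints" and adds that "McNemar's tests may be employed for categorical endpoints". It does not define 'adequate', name the categorical endpoints or give a significance level.

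SAP 2.1 fixes unequal periods: "The Optiflux Period is 12 HD treatments (visits 1 to 12) on the Optiflux dialyzer", whereas "The Endexo period is 38 HD treatments on the dialyzer with Endexo (approximately 13 weeks in duration". Permitted misses change this little: "A maximum of two missed treatments are permitted within visits 2 to 11" and "A maximum of four missed treatments are permitted within Visits 14-50". SAP 6.3 requires at least 36 Endexo treatments for the analysis population.

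SAP 5.1 acknowledges that "There are multiple observations of one measurement for each subject in each period" and deals with it by averaging within subject before analysis. The outcomes that could be treated as categorical are collected throughout each period: in SAP 4.2, "The number of any adverse events and device-related adverse events"; in SAP 4.3, a thrombus score for every dialyzer used. SAP 6.7 plans adverse events per treatment. SAP 6.8 plans each subject's proportion of fully clotted treatments, and also a count of subjects in each thrombus grade by period.

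**The concern.** McNemar's test takes one binary value per subject per period. The averaging rule in SAP 5.1 does not supply it, because the average of a repeated yes/no is a proportion and the average of a grade is a mean. The analyst must therefore choose a collapse that the SAP does not state. The most obvious choice is whether the subject ever had the event in the period, and the planned count of subjects per thrombus grade invites it.

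Under that choice a subject has 38/12 = 3.17 times as many opportunities on Endexo as on Optiflux. A significant excess of subjects with an adverse event or a clotted dialyzer on Endexo could then come from the visit schedule and be read as a property of the dialyzer.

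**Working it through.** **Inputs from the documents.** 12 and 38 treatments per subject (SAP 2.1); at least 36 Endexo treatments in the analysis population (SAP 6.3); 15 to 24 enrolled, aiming for at least 12 with 36 Endexo treatments (Protocol synopsis). The plan gives no error rate, power or discordance rate for any test, so there is no figure of its own to reproduce.

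**Assumptions.** The yes/no is any event in the period. Treatments are independent. The per-treatment risk p is the same on both dialyzers, so there is no dialyzer difference. The test is two-sided at 0.05. The documents give no event rates, so p is varied.

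**Formulas.** q1 = 1 − (1 − p)^12 for Optiflux and q2 = 1 − (1 − p)^38 for Endexo. P(event on Endexo only) = (1 − q1)q2; P(event on Optiflux only) = q1(1 − q2). The number of discordant subjects is binomial with n and the sum of these two. The rejection probability is found by enumerating all outcomes of the exact test.

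**Example, p = 3%.** q1 = 1 − 0.97^12 = 0.306 and q2 = 1 − 0.97^38 = 0.686. Endexo only: 0.694 × 0.686 = 0.476. Optiflux only: 0.306 × 0.314 = 0.096. Of the discordant subjects, 0.476/0.572 = 83% point against Endexo, where McNemar's null expects 50%.

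**Exact McNemar rejection with identical per-treatment risk, 12 v 38 treatments:**

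| p | q1 v q2 | n = 12 | n = 15 | n = 24 |
|---|---|---|---|---|
| 0.5% | 5.8% v 17.3% | 0.5% | 1.5% | 7.9% |
| 1% | 11.4% v 31.7% | 5.0% | 10.1% | 26.1% |
| 2% | 21.5% v 53.6% | 17.6% | 27.2% | 50.6% |
| 3% | 30.6% v 68.6% | 26.0% | 38.0% | 64.7% |
| 5% | 46.0% v 85.8% | 30.7% | 45.9% | 75.4% |
| 10% | 71.8% v 98.2% | 7.7% | 18.8% | 58.7% |
| 20% | 93.1% v 99.98% | 0.0% | 0.0% | 0.5% |

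To rounding, every rejection is against Endexo; a correct two-sided test would reject at most 2.5% in that direction. The rates fall at both ends because the exact test needs at least six discordant subjects (2 × 0.5^6 = 0.031). At p = 20% and n = 24 only about 24 × 0.069 = 1.7 are expected.

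**Sensitivity.**
- Uncorrected chi-square form at p = 1%, 2%, 5%: 21%, 33%, 51% (n = 12) and 37%, 60%, 83% (n = 24).
- 12 v 36 treatments, n = 24, exact, same risks: 23%, 45%, 71%.
- Very uneven subject risk (beta, shape 0.5), mean risk 1% to 5%, exact: 1% to 5% at n = 12 and 14% to 34% at n = 24.
- Equal windows of 12 v 12, p from 0.5% to 20%: at most 2.4% exact and about 5.1% chi-square. The inflation therefore comes from the unequal windows.

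**Check of replacement tests, again with no true difference (simulation).**
- A Cochran-Mantel-Haenszel (CMH) test stratified by subject holds 3% to 5% when a subject's risk is constant. If that risk varies between periods around the same mean, it rejects about 11% to 25% at an intra-period correlation of 0.05 to 0.10 (assumed).
- A paired sign-flip test on per-subject proportions of treatments rejects at most about 7% in the same settings.
- A paired t-test on those proportions, at constant risk, rejects 5% to 6% for p of 3% or more, but 8% to 11% at p = 1%.

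**The case against.** The strongest reply is that the harmful analysis is assumed. Neither document says that McNemar will be applied to any event in the period. A yes/no from one matched treatment per period would carry no exposure bias, and SAP 4.2 already pairs visit 1 with visit 13 for albumin and β2-microglobulin. This stands: the figures above are conditional on the collapse. What remains is that the SAP leaves the choice open and does not rule out the natural but misleading one.

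The SAP also already plans exposure-adjusted summaries of adverse events and full clotting. Averaged as SAP 5.1 requires, full clotting becomes a continuous proportion, for which SAP 5.2 offers the paired t-test. This too stands, and it supplies the fix. It does not say where McNemar would then apply, and the count of subjects per thrombus grade depends on exposure if a subject is counted at any occurrence.

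The stakes are low. The study is descriptive, the primary endpoint (Kuf) is measured on Endexo only, the test is doubly optional, and the Protocol synopsis names no between-period test.

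A reader might infer that McNemar is invalid here because it requires equal exposure, or that it cannot handle more than two grades. Neither is right. It validly tests equality of the two period-level probabilities; what fails is reading the result as a difference in per-treatment risk. Multi-category extensions exist (Bowker, Stuart-Maxwell).

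**Conclusion.** The point holds as a minor one. SAP 5.2 names McNemar as its only between-period test for categorical endpoints, leaves the yes/no undefined, and sits beside periods whose lengths differ threefold. Under the any-event collapse with identical per-treatment risks of 1% to 5%, the exact test rejects in 5% to 31% of trials at n = 12 and 26% to 75% at n = 24, almost always against Endexo.

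These sizes rest on the assumed collapse, assumed risks, independent treatments and a two-sided 5% level. They shrink to nothing for very rare events with few subjects, for very common events, and at n = 12 when risk is very uneven between subjects.

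A reader might infer that the trial's 5% error rate fails, or that its conclusions are biased against Endexo. The documents do not support that: they set no error rate, commit to no between-period test and tie no success criterion to one.

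**What to change.** In SAP 5.2, replace McNemar for outcomes observed over a whole period with a within-subject comparison of exposure-adjusted values, using a paired sign-flip permutation test or a signed-rank test. The values follow from SAP 5.1, 6.7 and 6.8: each subject's proportion of treatments with full clotting, adverse events per treatment (computed per subject), and mean thrombus grade. Keep McNemar only for a yes/no taken from one matched treatment per period (for example visit 1 v visit 13) or from equal-length windows, and state the endpoint, the cut-point and the significance level.

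A subject-stratified CMH test should not be the default, because it rejects too often when events cluster within a period.

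The cost is a few sentences in the SAP and no new data. The downside is that the paired test has low power for rare events, and it is approximate because the two proportions rest on different numbers of treatments.
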